## **9.2 TOXICITY MANAGEMENT FOR LABORATORY ABNORMALITIES**

Grade 3 and 4 laboratory abnormalities should be confirmed by repeat testing preferably within 3 calendar days of receipt of results and before study drug discontinuation, unless such a delay is not consistent with good medical practice. All laboratory abnormalities that would lead to a change in treatment should be confirmed as soon as possible.

### **9.2.1 Increases in Values for Liver Function Tests**

#### **9.2.1.1 Asymptomatic**

For asymptomatic Grade 3 elevations of total bilirubin, AST, ALT, or alkaline phosphatase, study treatment may be continued at the discretion of the site investigator in consultation with the Study Chair. Alternatively, the investigator may make substitutions to the antiretroviral regimen upon consultation with the Study Chair.

If asymptomatic abnormalities in liver enzymes of Grade 3 persist for more than 4 weeks, the site investigator should consider temporary interruption of study treatment in consultation with the Protocol Chair.

#### **9.2.1.2 Symptomatic or Grade 4**

For symptomatic Grade 3 elevations of total bilirubin, AST, ALT, or alkaline phosphatase or for Grade  $> 3$  elevations in AST, ALT, or alkaline phosphatase, all study treatment should be interrupted until the toxicity returns to Grade  $\leq 2$  or baseline, after which time all study treatment may be resumed.

If asymptomatic liver enzyme elevations Grade  $> 3$  or symptomatic liver enzyme elevations persist for more than 4 weeks, despite the interruption of all study treatment, or if liver function abnormalities recur to Grade  $\geq 3$  at any time after the resumption of study treatment, then all study treatment should be interrupted or discontinued and the Study Chair should be contacted regarding the reintroduction of study treatment or the selection of alternate ART.

## **9.2.2 Lipase**

#### **9.2.2.1 Grade $\geq 2$ Asymptomatic**

If a Grade  $\geq 2$  elevation of lipase occurs, the subject should be evaluated for signs and symptoms of pancreatitis and additional diagnostic evaluation should be performed as clinically indicated. For asymptomatic Grade 2 or 3 elevations of lipase, study treatment may be continued at the discretion of the site investigator in consultation with the Protocol Chair. Alternatively, the investigator may choose to substitute another antiretroviral agent for any of the components of the original study regimen. If Grade  $\geq 3$  toxicity persists for more than 14 days despite interruption or substitution of study treatment, or recurs after reintroduction of study treatment, all study treatment should be permanently discontinued, and a new potent antiretroviral regimen should be selected at the discretion of the local investigator when

appropriate resolution of pancreatitis occurs.

Subjects with Grade 4 elevations in serum lipase without clinical symptoms of pancreatitis should have all study treatment interrupted until the toxicity returns to Grade < 1, then all study treatment or a substituted regimen may be restarted at full dose.

#### **9.2.2.2 Symptomatic Pancreatitis (Regardless of Lipase Grade)**

A diagnosis of pancreatitis should be considered if clinical symptoms such as nausea, vomiting, or abdominal pain are present. Subjects with these signs and symptoms should be evaluated for the presence of pancreatitis through the use of diagnostic testing, which should include serum amylase, lipase, and triglyceride measurements and may include pancreatic imaging via abdominal ultrasound and/or CT scanning as clinically warranted. If a diagnosis of pancreatitis is confirmed, all study treatment should be interrupted immediately.

#### **9.2.3 Triglycerides/Cholesterol**

Subjects with asymptomatic triglyceride elevations Grade > 3 may continue to receive study treatment at the discretion of the local investigator. In consultation with the Protocol Chair, the On-Site Principal Investigator may consider the addition of permitted lipid-lowering agents if necessary to treat hyperlipidemia. Dose interruptions or discontinuations of study treatment should be considered only for confirmed increased fasting triglycerides  $\geq 1200$  mg/dL.

Elevations in triglycerides  $\geq 1200$  mg/dL: For subjects with a nonfasting triglyceride level  $\geq 1200$  mg/dL, a fasting triglyceride level and a serum amylase and lipase must be obtained. For Grade  $\geq 2$  asymptomatic elevations in serum amylase and/or lipase (collected in response to elevated triglycerides) in the setting of Grade > 3 hypertriglyceridemia, subjects should be started on a fibrate, and amylase and lipase should be monitored every 2 weeks until amylase and lipase are Grade < 2. If symptoms of pancreatitis develop, study treatment should be interrupted until pancreatitis resolves, amylase, and lipase are Grade < 2 and hypertriglyceridemia is Grade < 3. Consideration should be given to continuing a fibrate if study treatment is reintroduced.

Subjects may continue on all study treatment despite Grade  $\geq 3$  triglyceride elevations if they remain asymptomatic with close clinical follow-up. In consultation with the Study Chair, the concomitant administration of gemfibrozil, clofibrate, or fenofibrate may be considered.

If Grade 4 triglyceride toxicity persists 4 weeks after the addition of medical intervention (addition of lipid-lowering agent), all study treatment should be interrupted. If Grade 4 toxicity persists for more than 14 days after all study treatment has been interrupted, consider permanent discontinuation of all study treatment and a new potent antiretroviral regimen should be selected at the discretion of the local investigator in consultation with the Study Chair.

#### **9.2.4 Hyperglycemia**

Appropriate dietary modifications and glucose-lowering agents should be initiated for subjects with hyperglycemia, at the discretion of the local investigator and in accordance with customary medical care.

#### **9.2.5 Renal Insufficiency**

Tenofovir DF substitution should occur for a confirmed creatinine clearance  $< 50$  ml/min until an underlying etiology is determined. If no other etiology is determined or the renal insufficiency improves with holding tenofovir DF, tenofovir DF should be permanently discontinued.

Baseline serum creatinine will be the mean of the screening and entry values. If at any time serum creatinine is increased  $>1.5$ -fold above baseline, the serum creatinine should be repeated as soon as possible (preferably within one week). Participants with confirmed serum creatinine increases  $>1.5$ -fold above baseline should undergo an evaluation for potential causes of decreased renal function. Participants with confirmed increase in serum creatinine  $>1.5$ -fold above baseline should have serum creatinine monitored more frequently, at the discretion of the site investigator, until serum creatinine either stabilizes or decreases to  $\leq 1.5$ -fold above baseline. Drug dosing adjustments should be done based on the calculated creatinine clearance.

#### **9.2.6 Hypophosphatemia**

For Grade 1 and Grade 2 hypophosphatemia, phosphorus should be repeated as soon as possible (within 2 weeks is optimal), and tenofovir DF may be continued without other signs of renal tubular acidosis at the discretion of the site investigator.

For asymptomatic Grade 3 decreases in phosphorus, subjects may either substitute another nucleoside reverse transcriptase inhibitor (NRTI) for tenofovir DF, or may remain on tenofovir DF with the following caveats. Subjects should be treated with oral phosphate supplements and phosphorus levels should be re-tested weekly until phosphorus returns to Grade 2 or better. If Grade 3 or worse phosphorus levels persist, tenofovir DF should be discontinued and another NRTI should be substituted. If Grade 4 hypophosphatemia occurs, tenofovir DF should be changed to an alternative NRTI in consultation with the Protocol Chair, and serum phosphorus levels should be followed weekly until resolution to Grade 2 or better.

### **9.3 FOR ALL OTHER GRADE 3 OR 4 TOXICITY**

Subjects who develop a Grade 3 adverse event or toxicity reasonably causally related to the study medications (with the exception of asymptomatic laboratory abnormalities) should have all their antiretroviral study medication held and the subject rechecked each week until the adverse event returns to Grade  $< 2$ . If the investigator has compelling evidence that the adverse event has not been caused by the study medication or has another acceptable management plan, dosing may continue after discussion with the Protocol Chair. Once the adverse event is Grade  $< 2$ , the medications may be reinstated at full dose. If the adverse event recurs after 4 weeks, the above management scheme may be repeated.

Subjects who develop a Grade 4 adverse event or toxicity (with the exception of asymptomatic laboratory abnormalities) should have all antiretroviral medication discontinued. The subject should be followed weekly until resolution of the adverse event and encouraged to complete the protocol study evaluations. Further management of antiretrovirals should proceed at the site investigator's discretion.

Subjects with Grade 3 or 4 asymptomatic laboratory abnormalities may continue therapy if the investigator has compelling evidence that the toxicity is not related to study drug, following discussion with the sponsor and the Protocol Chair.

## **10 CRITERIA FOR DISCONTINUATION OF THE TREATMENT PROVIDED BY THE STUDY**

### **10.1 PERMANENT TREATMENT DISCONTINUATION**

- Drug-related toxicity (see section 9.0 Toxicity Management);
- Requirement for prohibited concomitant medications (see Section 5.3.3.);
- Clinical reasons believed life threatening by the Study Medical Director, even if not addressed in the toxicity management of the protocol;
- Suboptimal virologic response as defined in Section 4.4.;
- Subject repeatedly non adherent, to the extent that the physician believes it would not be in the subject's best interest to continue treatment;

The subjects who permanently discontinue treatment provided by the study according to the criteria described should continue a different ART regimen according to the standard of care currently in place. The study investigators will take necessary steps to ensure that the subjects continue on ART. Counseling will be provided with special emphasis on safety, and on efficacy of ART options to use in the future if the participant discontinues study ART, and does not continue with any other antiretroviral treatment.

### **10.2 PREMATURE STUDY DISCONTINUATION**

- Request by the subject to withdraw;
- Request of the primary care provider if s/he thinks the study is no longer in the best interest of the subject;
- Subject judged by the investigator to be at significant risk of failing to comply with the provisions of the protocol as to cause harm to self or seriously interfere with the validity of the study results;
- At the discretion of the Ministry of Health or National Institute of Health of Peru, any of the IRBs/ECs responsible for oversight of the study, study sponsor, or On-Site Principal Investigator.

## **11 STATISTICAL CONSIDERATIONS**

The overall aim of this project is to model seek-test-treat-retain strategies that specifically intervene to reduce HIV transmission through reductions in HIV-1 viral load and sexual risk behavior among individuals with early HIV infection, including both acute and recent infections.

### **11.1 OBJECTIVES**

#### **11.1.1 Primary Objectives**

1. To estimate the impact of immediate and deferred (6 months after diagnosis) ART on the decay dynamics of HIV viral load in plasma, semen and rectal secretions from individuals with early HIV infection;

2. To investigate the impact of drug and alcohol use on HIV transmission by examining and modeling the role of MSM and transgender women with substance abuse disorders in transmission clusters identified through partner tracing and phylogenetic analysis.

#### **11.1.2 Secondary Objectives**

1. To determine HIV incidence and associated risk factors among high-risk HIV-1 uninfected MSM and transgender women who participate in a program of frequent routine HIV testing.
2. To attempt to identify transmission clusters in phylogenetic trees constructed using early viral specimens from study participants with acute or recent HIV infection.
3. To determine other characteristics (self-reported sexual risk behavior, partner characteristics, use of entertainment venues, and method of referral for HIV testing) in MSM and transgender women within clusters compared to those outside of clusters.
4. To assess the feasibility and acceptability of re-contacting HIV seronegative individuals with evidence of acute infection (HIV-1 RNA positive) for further HIV testing and linkage to care.
5. To evaluate the frequency of HIV testing among recent sexual partners of participants diagnosed with early HIV-1 infection, comparing strategies such as partner tracing and notification, and general and targeted community outreach.
6. To evaluate retention in care, including adherence to ART and study procedures, among individuals with early HIV-1 infection receiving immediate and deferred ART.

### **11.2 ENDPOINTS**

#### **11.2.1 Primary Endpoints**

1. To quantify HIV viral load in plasma, semen and rectal secretions in individuals with early HIV infection in immediate versus deferred treatment groups.
2. To identify transmission clusters through phylogenetic analysis among participants with early HIV infection receiving immediate and deferred ART; Construction of models to assess the potential population impact of a seek-test-treat-retain strategy.

#### **11.2.2 Secondary Endpoints**

1. To identify associated risk factors for incident HIV-1 infection.
2. To identify sequence clusters using phylogenetic analysis among participants with early HIV infection.
3. To compare self-reported sexual risk behavior, partner characteristics, entertainment venue attendance, and method of referral in MSM and transgender women within clusters to those outside of clusters.

4. To determine the proportion of individuals with evidence of acute infection (HIV-1 RNA-positive) who are successfully contacted for confirmatory HIV testing and are then linked to care.
5. To determine the proportion of newly identified HIV-positive men willing to name at least one recent sexual partner, and the proportion of named partners subsequently contacted and tested.
6. To determine the proportion of men retained in care, including adherence to ART and study procedures, among individuals with early HIV-1 infection receiving immediate and deferred ART.

### **11.3 SAMPLE SIZE AND ACCRUAL**

Our goal is to enroll approximately 75-90 men with AHI and 75-90 with RHI in three years, with a target of enrolling 25-50 men with AHI and 25-50 men with RHI per year, or approximately 2-4 men in each group per month. We expect that another 50 men will be identified with acute or recent HIV-1 infection who will either not meet all inclusion requirements or who will not consent to enrollment in the study. Specimens for sequencing will be collected from all men.

Samples for sequencing will be obtained from all identified HIV+ partners of the 200 men with acute/recent infection (we anticipate that not all men will consent to partner tracing). Our initial sequencing efforts will focus on the 100 acutely infected men (75 enrolled plus 25 non-enrolled in immediate/deferred ART study) and their HIV+ partners (especially those with acute or recent HIV infection), testing a total of 400 samples. The first available sample will be sequenced with 454/pyrosequencing and analyzed as described below.

Semen HIV VL will be measured in samples from 60 (30 acute/30 recent) men in the immediate ART group and 60 (30 acute/30 recent) men in the deferred treatment group using established procedures in The University of Washington Virology Laboratory [177, 178]. We will seek separate funding to analyze additional samples, including rectal secretions.

### **11.4 MONITORING**

All endpoints will be calculated and monitored on a monthly basis throughout the period of enrollment and treatment.

### **11.5 ANALYSES**

#### **11.5.1 Viral Phylogenetic Analysis**

Viral phylogenetic analysis will be conducted to investigate the occurrence of clustered transmission during AHI as evidenced by detection of highly related sequences among men with acute infection [162, 179, 180] and their recent partners identified through contact tracing. An algorithm for identifying HIV transmission linkages among partnerships has recently been developed by our collaborator [name], who analyzed sequences using phylogenetic techniques and developed a Bayesian algorithm to evaluate the probability of linkage using genetic distance measurements [181]. The same approach will be used here and applied for the first time to identifying transmission clusters.

Next-generation deep sequencing using the 454/Pyrosequencing platform will be used to generate envelope gene sequences from each study participant using plasma from the first available time point following infection. Deep sequencing provides us with the opportunity to identify relatively low-frequency variants in each infection. This is important because we have found that in a significant fraction of the cases, divergent, low-frequency variants are often involved in transmission to a new host [181]. To provide context for the identification of linked transmissions, we will prepare two HIV-1 envelope gene sequence databases corresponding to the same genetic region as Lima. The first dataset will contain all available Peruvian HIV-1 sequences from the Los Alamos National Laboratory HIV Sequence Database (HIVDB) (<http://www.hiv.lanl.gov/content/sequence/HIV/mainpage.html>), as well as subtype B sequences from other countries in South America. This will enable us to determine the expected spread of genetic relationships from individuals without epidemiologic linkage. Second, a “linked” database of corresponding HIV-1 envelope gene sequences from 147 known transmission pairs [181] will be generated to enable us to determine the expected spread of genetic relationships from individuals with known epidemiologic linkage. HIV-1 linkage will be assigned by requiring the following: 1) pair derived HIV-1 env sequences from two or more individuals form monophyletic clusters (i.e., originating from the same terminal node) in maximum-likelihood phylogenetic trees that include all available sequences from unrelated individuals and 2) the pairwise genetic distances are required to be associated with a Bayesian posterior probability >50%. Pairs of sequences that meet these two requirements are tentatively classified as linked. In this manner, a phylogenetic tree containing clustered and unclustered sequences will be constructed for all acutely infected index cases and their HIV+ recent sexual contacts. These clusters are due to high-level transmission which occurs early after infection, before sequence divergence. (If funding allows or additional funding is available, specimens from men with recent infection and their partners will be sequenced and added to this analysis.)

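### Section 11.5.1 reads every phylogenetic link between an acutely infected man and a contact as early transmission, although the linkage rule ignores the contact's stage of infection

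*Combined protocol and SAP*

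**What the plan says.** Section 11.5.1 gives the purpose of the phylogenetic analysis as "to investigate the occurrence of clustered transmission during AHI as evidenced by detection of highly related sequences among men with acute infection" and their traced recent partners. Linkage needs two things. The sequences must "form monophyletic clusters (i.e., originating from the same terminal node) in maximum-likelihood phylogenetic trees", and "the pairwise genetic distances are required to be associated with a Bayesian posterior probability >50" per cent. Pairs that meet both are tentatively called linked. The tree is built "for all acutely infected index cases and their HIV+ recent sexual contacts", and the section then interprets the result: "These clusters are due to high-level transmission which occurs early after infection, before sequence divergence".

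Section 11.3 sets the sampling: "Samples for sequencing will be obtained from all identified HIV+ partners of the 200 men with acute/recent infection". It adds: "Our initial sequencing efforts will focus on the 100 acutely infected men (75 enrolled plus 25 non-enrolled in immediate/deferred ART study"), together with their HIV-positive partners. Partners with acute or recent infection have priority, but others are not excluded. The total is 400 samples.

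Section 11.5.2 summarises the number and size of clusters, the percentage of people in them and the longest window for onward transmission in each. It compares substance use and behaviour between clustered and unclustered people, using trees with and without partners.

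**The concern.** Neither linkage condition contains a stage or a date. The interpretive sentence supplies the stage by assertion.

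An acutely infected man was infected very recently, so his virus has had little time to diverge and his true source can link to him whatever that source's stage. Section 11.5.1 also adopts deep sequencing partly so that transmissions founded by divergent, low-frequency variants are not missed, which makes links to diversified, longer-standing infections more likely to be found. The 147 reference pairs used for calibration carry no stated restriction to early-stage sources. The background (Section 3.5.3) is more careful about similar clusters in Montreal, saying only that they may come from acute and early infection.

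Identifying clusters is part of primary endpoint 2, and cluster membership defines the groups in the substance-use comparison behind primary objective 2. If clustered men include some who acquired HIV from established infections, the cluster counts cannot be read as acute-phase transmission. A substance-use difference would then mix acquisition from established sources with early onward transmission.

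**Working it through.** The plan gives no error rate or expected yield for the linkage rule, so there is no figure to reproduce. The argument is first one of logic, then of scale.

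**Logic.** Take a linked pair: an acute index man and a contact whose infection was established before the index man was infected.
- The index man cannot be the contact's source, because the contact was infected first.
- If the link is direct, the contact is the source and transmitted from established infection.
- If the link is indirect, through a third person, it is still not onward transmission from the index man's acute phase.
- The rule counts the pair in each case, because it looks only at tree position and genetic distance.

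**How common such contacts might be.** Section 11.5.4 expects 300 seropositive men a year, about 10% of them recent, plus 30-45 acute.
- Not recent: 300 × 0.90 = 270.
- Share of all HIV-positive men found: 270/345 = 78% to 270/330 = 82%.
- Partner samples, at one per person: 400 − 100 = up to 300.
- If partners resembled the men found: 300 × 0.78 to 300 × 0.82, or about 235-245 samples from people with established infection.

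Partners need not resemble these men, and the priority for early-stage partners would lower the figure. Established contacts are nevertheless not an edge case.

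**Illustrative size.** Inputs: n = 100 index men (75 + 25, Section 11.3). Assumed: p, the share of index men whose true source is traced and sequenced; s, the probability that a true pair meets the rule, 0.7-0.9; and e, the share of sources with established infection. Assuming p and s do not vary with the source's stage, the expected number of misread index men is n × p × s × e. With e = 1:

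| p | s = 0.7 | s = 0.9 |
|---|---|---|
| 2% | 1.4 | 1.8 |
| 5% | 3.5 | 4.5 |
| 10% | 7 | 9 |
| 20% | 14 | 18 |
| 30% | 21 | 27 |

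The figures scale in proportion to e. With half the sources established, the 10% row becomes 3.5-4.5.

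**After staging.** Suppose a link counts only when the contact is staged acute or recent, and a fraction m of established contacts is mis-staged. The expected number becomes n × p × s × e × m. At p = 10% and e = 1, the 7-9 falls to 0.07-0.09 with m = 1% and to 0.35-0.45 with m = 5%. Two acute men who share an unsampled established source are not removed by this step.

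**The case against.** The plan is not blind to timing. It gives priority to early-stage partners, reports transmission windows by cluster, and plans trees without partners, which exclude the acute-to-established-partner links at issue. Links are only tentative, the analysis is descriptive, and no randomised comparison uses it.

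All of this is true, and it limits the severity. It does not rescue the sentence. The priority is not a restriction, and the window summary classifies nothing. The trees without partners are specified for the behaviour and substance-use comparison, and two men in them may still share an unsampled established source. The word tentative qualifies linkage, not stage.

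Three stronger readings are tempting, and the documents do not support them.
- A reader might infer that the rule would almost surely signal acute-phase transmission even if none occurred. The plan has no test based on at least one cluster, and the probability rests on an unstated yield y = p × s. With 100 men, 1 − (1 − y)^100 is 63% at y = 1% and reaches 99% only at about 4.5%.
- A reader might infer that the analysis gives the same answer whether acute-stage sources cause no infections or most. Cluster counts, cluster sizes and the trees without partners could differ between those situations.
- A reader might infer that the population model is biased by these counts. Section 11.5.4 takes infectivity from viral load and builds the force of infection from partners, acts and per-act probabilities. Phylogenetics supplies sexual-network data, and no count of acute-phase clusters is said to enter.

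**Conclusion.** The interpretive sentence in Section 11.5.1 does not follow from the linkage rule, and it should be corrected. This part needs no numerical assumption: the rule has no stage term, contacts of any stage are in the tree, and a link to an already established infection is not onward transmission from the index man's acute phase.

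The direction of error is towards overstating acute-phase transmission. Its size is unknown. The illustration of about 7-9 of 100 index men assumes that every source is established, 10% of sources are traced and sequenced, and sensitivity is 0.7-0.9. Section 11.3 says only that not all men are expected to consent to tracing.

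Severity: should fix. The remedy is cheap and the interpretation of a primary endpoint benefits, but the analysis is exploratory and separate from the randomised viral-load comparison.

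**What to change.** In Section 11.5.1, delete the sentence on early transmission, or qualify it to say that clusters may include acquisition from established infection. Classify links and clusters by every member's stage and available test dates, judged as of the index man's infection:
- (a) all members acute or recent with overlapping infection windows: compatible with early transmission;
- (b) any member with established infection: not counted as transmission during acute infection;
- (c) any member undated, and none known to be established: reported separately.

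Base the acute-phase statement on (a), with a sensitivity range that adds (c). Do not call (a) an upper bound. Shared established sources inflate it, but early-stage partners who cannot be dated deflate it: Section 5.3.2 requires a negative test in the previous three months for recent infection, and a traced antibody-positive partner may have none. Repeat the substance-use comparison by class, alongside the planned trees with and without partners.

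The cost is SAP wording and one derived variable, with no new visits. The acute, recent and chronic categories already exist for screened participants (Sections 5.3.2 and 7.2.1). For partners, the documents describe offers of testing, samples and data but not dating of infection, so available partner test dates would have to be recorded. Fewer clusters will count as early transmission, so that estimate will be less precise, and some partners will remain unstaged.
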